6.12. Acceptability and Palatability Analysis

Acceptability and palatability data will be collected and analyzed to address secondary and exploratory objectives of this study. The detail will be described by Lilly in separate acceptability and palatability analysis plans.

6.13. Health Outcomes/Quality-of-Life Analyses

Besides the health outcomes/ QOL measures discussed in Section 6.10.2 and Table JAHV.6.3. The change from baseline in European Quality of Life-5 Dimensions–Youth version (EQ-5D-Y) scores by treatment periods with the corresponding analysis population will be analyzed as exploratory analyses using methods described for continuous or categorical data as described for efficacy measures. The EQ-5D-Y will be scored according to the EQ-5D-Y user guide (Van Reenen et al. 2014).

Change from baseline in the individual scales (Global Health; Physical Functioning; Role/Social Limitations-Physical; Role/Social Limitations-Emotional/Behavioral; Bodily Pain/Discomfort; Behavior; Global Behavior Item; Mental Health; Self-Esteem; General Health Perception; Change in Health; Parental-Impact-Time; Parental Impact-Emotion; Family-Activities; Family-Cohesion) as measured by the CHQ-PF50 by treatment group during the DBW period will also be included as exploratory analyses. The individual scales of the CHQ-PF50 will be scored according to the manual, “CHQ Scoring and Interpretation manual”. (HealthActCHQ 2013).

6.14. Bioanalytical and Pharmacokinetic/Pharmacodynamic Methods

Pharmacokinetic, pharmacodynamic and biomarker analyses to address secondary and exploratory objectives of this study will be described by Lilly in separate PK/PD and Biomarker analysis plans.

6.15. Evaluation of Immunological Measures

Change from baseline in immunoglobulin levels and peripheral blood immunophenotyping (including T and B cells, T cell subsets, and natural killer [NK] cells) at Weeks 4, 12, and at the end of the DBW period will be evaluated and summarized using descriptive statistics. Patients who are immunized with TDaP or pneumococcal conjugate vaccines will have their immunoglobulin G (IgG) antibody titers to the antigens evaluated preimmunization and at 4 and 12 weeks postimmunization. A primary immune response will be assessed in patients who have never received TDaP or pneumococcal conjugate vaccines previously, and secondary/booster responses will be assessed if the patients have previously received the vaccines.

6.16. Subgroup Analysis

Cox proportional hazards regression will be used to evaluate the similarity of treatment effect across the JIA categories (polyarticular and extended oligoarticular [combined] versus ERA and JPsA [combined]). The model will have treatment and stratification variables as factors in the model. If any of these variables are redundant for a particular model, they will be dropped.

For the primary endpoint, selected secondary endpoints, and selected growth measurements, following subgroup analysis may be conducted:

- Gender: (Male; Female)
- Age group (12 to <18 years, 9 to <12 years, 6 to <9 years, 2 to <6 years)
- Geographic region (Asia, South America, Europe and rest of world)
- JIA categories (polyarticular and extended oligoarticular [combined] versus ERA and JPsA [combined])
- JIA categories (polyarticular, extended oligoarticular, ERA, JPsA)
- Predose exposure ESR categories (elevated [>20 mm/hour] and not elevated)
- history of prior bDMARD use (Yes or No)
- MTX usage at baseline (Yes or No)

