5.2. Number of Participants

Approximately 197 patients will be enrolled with at least 128 patients (at least 10 patients with ERA [including JPsA]) randomized to be evaluated for the primary endpoint in the DBW. The actual number of patients enrolled in the study may be adjusted upward or downward to allow for randomization of 128 patients.

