6.1.4. Analysis Methods

The primary endpoint will be the time-to-flare during the DBW period for randomized patients. Patients who discontinue or complete the DBW period without experiencing a flare will have their data censored at the time of their discontinuation date or completion date. The censored patients will contribute to the at-risk set in the stratified logrank test. Survival curves will be estimated using the Kaplan–Meier method in the DBW period. Treatment comparisons will be performed using a stratified log-rank test across JIA categories (polyarticular and extended oligoarticular [combined] versus ERA and JPsA [combined]) for the DBW population in the DBW period. Treatment comparisons may also be analyzed using a Cox proportional hazards model adjusted for stratification variables. The hazard ratio with 95% CIs will be reported. And the similarity of treatment effect across JIA categories (polyarticular and extended oligoarticular [combined] versus ERA and JPsA [combined]) will be evaluated using Cox proportional hazards regression adjusted for stratification variables. If any of these variables are redundant for a particular model, they will be dropped.

Secondary efficacy and health outcomes analyses ([Table JAHV.6.4](#) and [Table JAHV.6.5](#)) will be based on treatment period and respective study populations.

Efficacy, health outcomes, and safety data collected in OLLI period will be summarized without inferential statistics.

In the DBW period, the main analysis of categorical efficacy variables and health outcomes variables will use a logistic regression analysis with treatment, JIA categories (polyarticular and extended oligoarticular [combined] versus ERA and JPsA [combined]), predose exposure ESR categories (elevated [>20 mm/hour] and not elevated), history of prior bDMARD use (Yes or No) as covariates in the model. The p-value and 95% CI for the odds ratio from the logistic regression model are used for statistical inference.

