In the DBW period, the main analysis for all continuous efficacy and health outcomes variables will use analysis of covariance (ANCOVA) model with treatment, JIA patient categories (polyarticular and extended oligoarticular [combined] versus ERA and JPsA [combined]), predose exposure ESR categories (elevated [>20 mm/hour] and not elevated), history of prior bDMARD use (Yes or No), and baseline score as covariates in the model. For ESR and high-sensitivity C-reactive protein (hsCRP) analysis, predose ESR level categories will not be included as a covariate. Type III sums of squares for the least-squares mean (LSM) will be used for the statistical comparison of treatment groups, and the LSM difference, standard error, p-value and 95% CI will also be reported. The LOCF approach will be used to impute missing data.

The mixed model repeated measures (MMRM) analysis will also be considered as a supplemental analysis method. The MMRM will use a restricted maximum likelihood (REML) estimation. The model will include treatment, JIA patient categories (polyarticular and extended oligoarticular [combined] versus ERA and JPsA [combined]), predose exposure ESR categories (elevated [>20 mm/hour] and not elevated), history of prior bDMARD use (Yes or No), visit, treatment-by-visit-interaction, baseline score and baseline-by-visit-interaction as fixed effects. If any of these are redundant for a particular model, they will be dropped. An unstructured (co)variance structure will be used to model the between- and within-patient errors. If this analysis fails to converge, the heterogeneous autoregressive [ARH(1)], followed by the heterogeneous compound symmetry (CSH), followed by the heterogeneous Toeplitz (TOEPH) will be used. The Kenward-Roger method will be used to estimate the degrees of freedom. Type III tests for the LSM will be used for the statistical comparison. The LSM difference, standard error, p-value, and 95% CI will also be reported.

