6.11. Planned Exploratory Analyses

In consideration of the limited sample size in JIA categories (polyarticular and extended oligoarticular [combined] versus ERA and JPsA [combined]), a non-stratified logrank test may be applied to analysis of time to flare as an exploratory analysis. The p-value and median time to flare (if applicable) by treatment group will be reported. Treatment comparisons may also be analyzed using a Cox proportional hazards model. The hazard ratio with 95% CIs will be reported. The Kaplan-Meier product limit method will be used to estimate the survival curves for time-to flare. Time-to flare will also be summarized graphically by treatment group using Kaplan-Meier techniques.

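### The Cox model that SAP 6.1.4 and 6.16 assign to checking whether the effect is alike in the two JIA categories has no treatment-by-category term, so as listed it can only return one shared hazard ratio

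*SAP*

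**What the plan says.** SAP 6.16 makes a firm commitment: "Cox proportional hazards regression will be used to evaluate the similarity of treatment effect across the JIA categories", with polyarticular and extended oligoarticular combined on one side and ERA and JPsA combined on the other. The next sentence gives the model: "The model will have treatment and stratification variables as factors in the model". A further sentence allows redundant variables to be dropped.

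SAP 6.1.4 makes the same commitment; the similarity question "will be evaluated using Cox proportional hazards regression adjusted for stratification variables". Just before that, it describes the overall comparison in matching terms: "Treatment comparisons may also be analyzed using a Cox proportional hazards model adjusted for stratification variables".

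SAP 6.16 then lists demographic and clinical subgroups, including JIA category in two-level and four-level form. For these, the "following subgroup analysis may be conducted", with no model, estimator or contrast.

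SAP 6.10.1 and 6.11 mention only overall Cox models. Protocol 10.3.3.1 and 10.3.9 add no by-category analysis of time to flare.

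**The concern.** The stated purpose and the stated model do not match. With treatment and JIA category entered as main effects, category shifts the baseline hazard and treatment has one coefficient. That coefficient is the fitted effect in both categories by construction, so it supports neither similarity nor difference.

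This is also the only subgroup question on flare that the SAP commits to with firm wording. The two categories are a randomisation stratum and the stratum of the primary test, so readers will ask about consistency between them. If the contrast is left unstated, it may be chosen after the data are seen, or the shared hazard ratio may be presented as evidence that the effect is alike.

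**Working it through.** **1. The two model descriptions compared**

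| Analysis | Where | Terms stated |
|---|---|---|
| Overall treatment comparison (optional) | SAP 6.1.4, 6.10.1 | treatment, stratification variables |
| Similarity across JIA categories (committed) | SAP 6.1.4, 6.16 | treatment, stratification variables |

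As written, these are the same model. The SAP does spell out interactions elsewhere: the MMRM in 6.1.4 includes "visit, treatment-by-visit-interaction, baseline score and baseline-by-visit-interaction as fixed effects".

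**2. Inputs**

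SAP 5.2 gives 128 patients randomised 1:1, flare in 35% on baricitinib and 60% on placebo, dropout of at most 10%, and two-sided alpha of 0.05. Protocol 5.1.4 gives up to 32 weeks of follow-up. Protocol 5.2 gives a minimum of 10 ERA patients, counting JPsA. ERA/JPsA counts of 26 and 40 are assumptions.

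**3. The plan's own figure**

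HR = ln(0.65)/ln(0.40) = 0.470. Events = 128 × 0.90 × 0.475 = 54.7. The Schoenfeld formula gives 79.7% power, which agrees with the stated value of about 80%.

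**4. Two scenarios**

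- (a) HR 0.47 in polyarticular/extended oligoarticular; HR 1.0 in ERA/JPsA (60% flare in both arms).
- (b) 35% versus 60% in both categories, so HR 0.47 throughout.

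Expected flares per cell = patients in cell × flare rate × r, with r from 1.00 to 0.90 for 0% to 10% dropout. SE of the log ratio of hazard ratios = √(sum of 1/flares over the four cells). The 95% CI factor each way = exp(1.96 × SE).

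Example, (a) with 10 ERA/JPsA patients and r = 1: the cells are 59 × 0.35 = 20.65, 59 × 0.60 = 35.4, 5 × 0.60 = 3 and 3. SE = √(0.0484 + 0.0282 + 0.3333 + 0.3333) = 0.862, and the factor is 5.42.

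| ERA/JPsA patients | (a) ERA/JPsA flares | (a) SE | (a) CI factor | (b) ERA/JPsA flares | (b) SE | (b) CI factor |
|---|---|---|---|---|---|---|
| 10 | 5.4–6.0 | 0.862–0.909 | 5.4–5.9 | 4.3–4.8 | 0.991–1.044 | 7.0–7.7 |
| 26 | 14–16 | 0.587–0.619 | 3.2–3.4 | 11–12 | 0.661–0.697 | 3.7–3.9 |
| 40 | 22–24 | 0.519–0.547 | 2.8–2.9 | 17–19 | 0.574–0.605 | 3.1–3.3 |

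Chance that an ERA/JPsA arm has no flare when n = 10: A + B − AB, with A and B = (1 − rate × r)^5 for the two arms. This is 2%–4% in (a) and 13%–17% in (b).

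**5. What each model reports**

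Simulation: 1,200 trials per setting, exponential flare times, 10% dropout, flares dated to 4-weekly visits, Efron ties, covariates treatment and category.

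| ERA/JPsA patients | Shared HR in (a) | Shared HR in (b) | (a)/(b) | Median ratio of HRs in (a), interaction added | Interaction p<0.05 in (a) |
|---|---|---|---|---|---|
| 10 | 0.503 | 0.462 | 1.09 | 2.17 | 11.8% |
| 26 | 0.558 | 0.469 | 1.19 | 2.20 | 23.7% |
| 40 | 0.622 | 0.466 | 1.33 | 2.14 | 29.7% |

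The median ratios are among trials with a flare in both ERA/JPsA arms. Trials with an ERA/JPsA arm without flares count as not significant. The true ratio in (a) is 1/0.470 = 2.13.

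Precision of the shared HR, with all 128 at 35%/60%: SE = √(1/(22.4r) + 1/(38.4r)) = 0.266–0.280, a factor of 1.68–1.73. The gaps of 1.09 to 1.33 between (a) and (b) lie inside it.

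**6. Cross-checks**

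A separate simulation of 400 trials per setting gave shared HRs of 0.50, 0.57 and 0.62 in (a), and interaction significance in 11%, 24% and 26%. A single sample of 20,000 with an ERA/JPsA share of 40/128, adjusted also for prior bDMARD and ESR factors (simulated with no effect on flare), gave a shared HR of 0.62. Adding the interaction recovered 0.46 and 1.02.

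**The case against.** **Intent.** The analysis sits under a subgroup heading, its purpose is stated, and 6.1.4 treats it as distinct from the overall comparison. An analyst might well add the interaction or fit each category separately. That is plausible, and the authors may have meant it, but neither is written.

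**The redundancy sentence.** JIA category, and the ESR stratum that applies only to polyarticular patients, would become redundant in a within-category fit, so the sentence is compatible with separate fits. However, it only removes terms, and near-identical wording accompanies the MMRM in 6.1.4 and the general covariate text in 6.2.

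**The subgroup list.** By-category flare results are foreseen in 6.16. They are optional, name no contrast, and do not repair the committed analysis.

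**Low precision.** This objection stands in substance. Even the corrected analysis would detect complete loss of effect in ERA/JPsA in only about 12% to 30% of trials, and SAP 6.11 already acknowledges the difficulty ("In consideration of the limited sample size in JIA categories"). It limits the consequence. It is also the reason to show wide by-category intervals, because a single pooled value conceals them.

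**Assumptions.** The HR of 1.0 and the counts of 26 and 40 are illustrative. The floor of 10 is itself unclear: the Protocol synopsis attaches it to ERA alone, while 5.2 counts JPsA within it, so the combined category could be planned to be larger. The structural point needs none of these figures.

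**Conclusion.** The concern holds. Followed as written, the committed analysis cannot answer the question set for it, because a main-effects Cox model has one treatment effect by construction. That conclusion rests on the SAP's wording and on algebra.

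The size is illustrative. With no effect at all in ERA/JPsA, the listed output would still show a shared hazard ratio of about 0.50 to 0.62 for 10 to 40 such patients, against 0.46 to 0.47 when the effect is uniform. It cannot separate the two cases. These figures assume exponential flare times, the planned 35% and 60% rates, up to 10% dropout and the assumed category sizes.

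The practical consequence is limited. The analysis is supportive, its precision will be low however it is specified, and neither the primary stratified log-rank test nor the sample size is touched. It should be fixed because a stated commitment cannot be met as specified and the correction costs almost nothing.

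**What to change.** In SAP 6.1.4 and 6.16:

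- Add the treatment-by-JIA-category term to this Cox model.
- Report the hazard ratio with 95% CI in each category, and the ratio of hazard ratios with 95% CI, labelled descriptive.
- State that precision will be low and that a non-significant interaction is not evidence of similarity.
- If separate fits per category were intended, say so and name the contrast between them.
- Optionally, name a penalised or profile-likelihood interval for the case where an arm within a category has no flare.

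The cost is one model term and a few sentences across the two sections. No new data are needed and the primary analysis does not change.

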6.17. Analysis on Subsets of Patients

Additional analysis on subpopulation of patients may be conducted based on country or geographic region.

The summary statistical analysis will be conducted for the following subsets of patients at each visit.

In the subset of patients with JPsA:

- change from baseline in Psoriasis Area and Severity Index (PASI) score during the OLLI period and during the DBW period.

In the subset of patients with JPsA or ERA:

- change from baseline in Spondyloarthritis Research Consortium of Canada (SPARCC) index of enthesal assessment during the OLLI period and during the DBW period
- change from baseline in Juvenile Spondyloarthritis Disease Activity Index (JSpADA) during the OLLI period and during the DBW period

The detail of the calculation is documented in [Table JAHV.6.8](#).

Table JAHV.6.8. Description and Derivation of Endpoints for Subsets of Patient

Measure	Description	Variable	Derivation/Comment	Imputation approach if with missing components

Psoriasis Area and Severity Index (PASI)
	
Psoriasis Area and Severity Index (PASI) combines assessments of the extent of body-surface involvement in 4 anatomical regions (head and neck, trunk, arms, and legs) and the severity of scaling (S), redness (R), and plaque induration/infiltration (thickness, T) in each region, yielding an overall score of 0 for no psoriasis to 72 for the most severe disease (Fredriksson and Pettersson 1978). Severity is rated for each index (R, S, T) on a 0-4 scale (0 for no involvement up to 4 for severe involvement):
 
 0 = none 1 = slight 2 = moderate 3 = severe 4 = very severe 
The body is divided into four anatomical regions comprising the head (h), upper limb (u), trunk (t), and lower limb (l). In each of these areas, the fraction of total body surface area affected is graded on a 0-6 scale (0 for no involvement; up to 6 for 90% - 100% involvement):
 
 0 = 0% (clear) 1 = >0% to <10% 2 = 10% to <30% 3 = 30% to <50% 4 = 50% to <70% 	
PASI change from baseline
	
The composite PASI score is calculated by multiplying the sum of the individual-severity scores for each area by the weighted area-of-involvement score for that respective area, and then summing the four resulting quantities as follows: $PASI = 0.1(Rh + Th + Sh)Ah + 0.2(Ru + Tu + Su)Au + 0.3(Rt + Tt + St)At + 0.4(Rl + Tl + Sl)Al$
 
Where, Rh, Ru, Rt, Rl = redness score of plaques on the head, upper limb, trunk, and lower limb, scored 0-4 respectively; Th, Tu, Tt, Tl = thickness score of plaques on the head, upper limb, trunk, and lower limb, scored 0-4 respectively; Sh, Su, St, Sl = scaliness score of plaques on the head, upper limb, trunk, and lower limb, scored 0-4 respectively; Ah, Au, At, Al = numerical value translation of % area of psoriatic involvement score for the head, upper limb, trunk, and lower limb, respectively.
 
PASI scores are treated as a continuous score, with 0.1 increments within these values.
 
Calculated as: observed PASI minus
	
If any individual score is missing, the PASI score will not be calculated, hence, missing. LOCF will be applied

Measure	Description	Variable	Derivation/Comment	Imputation approach if with missing components
	
5 = 70% to <90% 6 = 90% to 100%
 
The various body regions are weighted to reflect their respective proportion of body surface area.
		
baseline PASI
	

Spondyloarthritis Research Consortium of Canada (SPARCC) enthesitis
	
SPARCC enthesitis is an index used to measure the severity of enthesitis (Maksymowych et al. 2009). The SPARCC assesses 16 sites for enthesitis using a score of “0” for no activity and “1” for activity. Sites assessed include Medial epicondyle (left/right [L/R]), Lateral epicondyle (L/R), Supraspinatus insertion into greater tuberosity of humerus (L/R), Greater trochanter (L/R), Quadriceps insertion into superior border of patella (L/R), Patellar ligament insertion into inferior pole of patella or tibial tubercle (L/R), Achilles tendon insertion into calcaneum (L/R), and Plantar fascia insertion into calcaneum (L/R).
	
SPARCC enthesitis change from baseline
	
The SPARCC is the sum of all site scores Range: 0–16, higher scores indicate more severe enthesitis.
 
Calculated as: observed SPARCC enthesitis score – baseline SPARCC enthesitis score
	
If any individual component is missing, the SPARCC score will not be calculated, hence, missing. LOCF will be applied

Juvenile Spondyloarthritis Disease Activity (JSpADA) Index
	
The JSpADA is used to evaluate the disease activity of juvenile spondyloarthritis (Weiss et al. 2014). The range of possible scores is 0 to 8, where higher scores indicate more disease activity.
	
JSpADA change from baseline
	
The Juvenile Spondyloarthritis Disease Activity Index scores will be determined by 8 components:
 
 • Active joint count: 0 joints = 0, 1 to 2 joints = 0.5, >2 joints = 1 • Active enthesitis count: 0 entheses = 0, 1 to 2 entheses = 0.5, >2 entheses = 1 • Pain over the past week as assessed using a 0-10 NRS (0 = no pain; 10 = pain as bad as your child can imagine): 0 = 0, 1 to 4 = 0.5, 5 to 10 = 1 	
If any individual score is missing, the JSpADA score will not be calculated, hence, missing. LOCF will be applied

Measure	Description	Variable	Derivation/Comment	Imputation approach if with missing components
			
 • CRP level related to juvenile spondyloarthritis activity: normal = 0, 1 to 2 times normal = 0.5, >2 times normal = 1 • Morning stiffness >15 minutes: Absent = 0, Present = 1 • Clinical sacroiliitis (defined as the presence of ≥ 2 of the following: tenderness on examination, positive Patrick’s test or flexion, abduction and external rotation (FABER) test, and inflammatory back pain): Absent = 0, Present = 1 • Uveitis (any uveitis including acute/symptomatic and chronic/asymptomatic disease): Absent = 0, Present = 1 • Back mobility (abnormal back mobility defined as modified Schober’s test <20 cm): Normal = 0, Abnormal = 1 
Total score= sum of 8 domain score
 
Calculated as: observed JSpADA score – baseline JSpADA score
	

Abbreviations: LOCF – last-observation-carried-forward.

Table JAHV.6.9. Description of Analysis Period and Analysis Method of Subsets of Patients Analysis

Variable	Population	Analysis Period	Treatment Comparisons	Analysis Method	Analysis Type
PASI change from baseline	For JPsA patient in OLLI2	Week 2 to Week 12	No comparison	Summary statistics	Secondary analysis
	For JPsA patient in DBW	Week 16 to Week 44	No comparison	Summary statistics by treatment group	Secondary analysis
SPARCC enthesitis change from baseline	For JPsA and ERA patient in OLLI2	Week 2 to Week 12	No comparison	Summary statistics	Secondary analysis
	For JPsA and ERA patient in DBW	Week 16 to Week 44	No comparison	Summary statistics by treatment group	Secondary analysis
JSpADA change from baseline	For JPsA and ERA patient in OLLI2	Week 2 to Week 12	No comparison	Summary statistics	Secondary analysis
	For JPsA and ERA patient in DBW	Week 16 to Week 44	No comparison	Summary statistics by treatment group	Secondary analysis

Abbreviations: DBW = double-blind withdrawal; ERA = enthesitis-related juvenile idiopathic arthritis; Psoriasis Area and Severity Index; JSpADA = Juvenile Spondyloarthritis Disease Activity Index; OLLI = open-label lead-in; SPARCC = Spondyloarthritis Research Consortium of Canada.

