
 • To evaluate the efficacy of baricitinib compared to placebo in children with JIA • To assess the efficacy of baricitinib in children with JPsA • To assess the efficacy of baricitinib compared to placebo in children with JPsA • To assess the efficacy of baricitinib in children with ERA or JPsA • To assess the efficacy of baricitinib compared to placebo in children with ERA or JPsA • To evaluate the potential effects of baricitinib on the cellular and humoral immune system 	
During the DBW period:
 
 • Proportion of patients with disease flare • PedACR30/50/70/90/100 response rates • Changes from baseline in each of the 6 individual components of the PedACR Core Set variables to the end of the DBW period (due to disease flare or completion) as follows: 
 o Number of active joints o Number of joints with limited range of motion o Physician’s Global Assessment of Disease Activity o Parent’s Global Assessment of Well-Being o Physical function as measured by the CHAQ o Acute-phase reactant (hsCRP) and ESR • Proportion of patients with inactive disease (as defined by Wallace et al. 2011) • Proportion of patients with minimal disease activity (as defined by Consolaro et al. 2012) • Proportion of patients in remission (as defined by Wallace et al. 2012) • Change from baseline in JADAS-27 • Change from baseline in the PhS and PsS of the CHQ-PF50 • Change from baseline in caregiver burden as measured by the Parental Impact-Time and Parental Impact-Emotion scales of the CHQ-PF50 • Change from baseline in arthritis-related pain severity as measured by the CHAQ pain severity VAS item • Change in Psoriasis Area and Severity Index (PASI) score during the OLLI period. • Change from baseline in PASI score during the DBW period • Change in Spondyloarthritis Research Consortium of Canada (SPARCC) enthesitis index during the OLLI period. • Change in Juvenile Spondyloarthritis Disease Activity Index (JSpADA) during the OLLI period • Change from baseline in SPARCC enthesitis index at during the DBW period • Change from baseline in JSpADA during the DBW period • Change in immunoglobulin levels and peripheral blood immunophenotyping (including T and B cells, T cell subsets, and NK cells) from baseline and at Week 4, Week 12, and Week 44 • Change of IgG titers from pre-vaccination to 4 weeks and 12 weeks post vaccination in patients eligible for vaccination with tDaP and/or pneumococcal conjugate vaccine according to local guidelines

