10.3.9. Subgroup Analyses

The summary statistical analysis will be conducted for the following subset of patients at each visit.

In the subset of patients with JPsA:

- Change from baseline in PASI score during the OLLI period and during the DBW period.

In the patients with JPsA or ERA:

- Change from baseline in SPARCC index of enthesal assessment during the OLLI period and during the DBW period.
- Change from baseline in JSpADA during the OLLI period and during the DBW period.

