
 • To evaluate the efficacy of baricitinib compared to placebo in children with JIA • To assess the efficacy of baricitinib in children with JPsA • To assess the efficacy of baricitinib compared to placebo in children with JPsA • To assess the efficacy of baricitinib in children with ERA or JPsA • To assess the efficacy of baricitinib compared to placebo in children with ERA or JPsA 	
During the DBW period:
 
 • Proportion of patients with disease flare • PedACR30/50/70/90/100 response rates • Changes from baseline in each of the 6 individual components of the PedACR Core Set variables (due to disease flare or completion) as follows: 
 ○ Number of active joints ○ Number of joints with limited range of motion ○ Physician’s Global Assessment of Disease Activity ○ Parent’s Global Assessment of Patient’s Overall Well-Being ○ Physical function as measured by the CHAQ ○ Acute-phase reactant (hsCRP) and ESR • Proportion of patients with inactive disease (as defined by Wallace et al. 2011) • Proportion of patients with minimal disease activity (as defined by Consolaro et al. 2012) • Proportion of patients in remission (as defined by Wallace et al. 2011) • Change from baseline in JADAS-27 • Change from baseline in the PhS and PsS of the CHQ-PF50 • Change from baseline in caregiver burden as measured by the Parental Impact-Time and Parental Impact-Emotion scales of the CHQ-PF50 • Changes from baseline in arthritis-related pain as measured by the CHAQ pain severity VAS item • Change in Psoriatic Area and Severity Index (PASI) score during the OLLI period • Change from baseline in PASI score during the DBW period • Change in Spondyloarthritis Research Consortium of Canada (SPARCC) enthesitis index during the OLLI period • Change in Juvenile Spondyloarthritis Disease Activity Index (JSpADA) during the OLLI period • Change from baseline in SPARCC enthesitis index during the DBW period • Change from baseline in JSpADA during the DBW period

Secondary Objectives and Endpoints

Objectives	Endpoints

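### Two secondary objectives call for a placebo comparison in JPsA and in ERA or JPsA, but SAP Table JAHV.6.9 plans per-arm description only and conflicts with SAP 6.1.4

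*SAP*

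**What the plan says.** **Objectives.** Protocol Section 4 (Table JAHV.4), the protocol synopsis and SAP 4.2 (Table JAHV.4.2) set out two pairs of objectives for these children. Each pair has a non-comparative member, tied to the open-label lead-in (OLLI), and a comparative member, tied to the DBW period. The comparative ones read "To assess the efficacy of baricitinib compared to placebo in children with JPsA" and "To assess the efficacy of baricitinib compared to placebo in children with ERA or JPsA". Their endpoints are "Change from baseline in PASI score during the DBW period" for JPsA, and "Change from baseline in SPARCC enthesitis index during the DBW period" and "Change from baseline in JSpADA during the DBW period" for ERA or JPsA.

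**Analysis of these endpoints.** Protocol 10.3.9 says: "The summary statistical analysis will be conducted for the following subset of patients at each visit". SAP 6.17 repeats this. All three DBW rows of SAP Table JAHV.6.9 show "No comparison" under treatment comparisons and "Summary statistics by treatment group" under method, while classing the rows as secondary analyses.

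**General rule.** SAP 6.1.4 assigns ANCOVA with a treatment term to all continuous efficacy and health outcome variables in the DBW period, with the least-squares mean difference, standard error, p-value and 95% CI reported. Protocol 10.3.1 also prescribes ANCOVA with treatment for continuous efficacy variables. Neither section exempts PASI, SPARCC or JSpADA.

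**The concern.** The placebo comparison is what separates the two DBW objectives from the OLLI objectives beside them, yet the table that assigns the method removes it. The general rule and the table also lead to different outputs: one programmer following 6.1.4 would produce a treatment difference, while another following Table JAHV.6.9 would not. If the choice is left until after unblinding, it can depend on the results.

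Two per-arm means of change from pre-treatment baseline do not isolate the effect of continuing rather than withdrawing baricitinib. Both arms enter the DBW period after about 12 weeks of open-label drug and were selected as responders, so both may show improvement. A reader given only those means has to form the contrast, and judge its precision, unaided.

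**Working it through.** **1. Objective against planned analysis.**

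| Comparative objective | DBW endpoint | Table JAHV.6.9 comparison | SAP 6.1.4 |
|---|---|---|---|
| JPsA | PASI change | none | ANCOVA, difference and 95% CI |
| ERA or JPsA | SPARCC change | none | ANCOVA, difference and 95% CI |
| ERA or JPsA | JSpADA change | none | ANCOVA, difference and 95% CI |

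Three of three endpoints conflict. Elsewhere the plan does compare: the DBW rows of SAP Table JAHV.6.5 specify baricitinib versus placebo, and exploratory mTSS gets an ANCOVA test of the treatment difference (SAP 6.11.1). SAP 6.16 does not fill the gap. Its Cox model concerns time to flare, and its subgroup analyses of selected secondary endpoints are optional.

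**2. What a per-arm change contains.** SAP 6.1.2 defines efficacy baseline (flare excepted) as the last value on or before the first baricitinib dose. Write B for that value, R for the value at randomization (Week 12) and V for the value at a DBW visit. In either arm,

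V − B = (R − B) + (V − R).

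The first term is the open-label response, present in both arms in children who had to reach PedACR30 to be randomized (Protocol 5.1.4, SAP 5.3). Only the second term reflects randomized treatment. In the difference between arms, the first term cancels in expectation because of randomization, which is stratified by JIA category (ERA and JPsA combined). In a per-arm summary it does not cancel.

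**3. Precision of the missing estimate.** The plan gives no sample size, effect size or power for these objectives, so there is no figure to reproduce. The one relevant number is the floor in Protocol 5.2: at least 10 randomized patients with ERA, JPsA included. Assume an even split into n per arm and work in units of the within-arm SD. The unadjusted 95% half-width is

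t(0.975, 2n − 2) × √(2/n).

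| n per arm | Degrees of freedom | Half-width (SD) |
|---|---|---|
| 5 (floor) | 8 | 2.306 × 0.632 = 1.46 |
| 10 (assumed) | 18 | 2.101 × 0.447 = 0.94 |
| 20 (assumed) | 38 | 2.024 × 0.316 = 0.64 |

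ANCOVA with treatment and baseline score uses one more degree of freedom. At n = 5 that leaves 7, giving 2.365 × 0.632 = 1.50 SD before any gain from the covariate.

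No minimum is stated for JPsA alone, so none of these rows can be applied to PASI.

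**4. Power if a formal test were wanted.** At 5 per arm, two-sided 0.05, two-sample t-test power is 11%, 20% and 29% for true differences of 0.5, 0.8 and 1.0 SD (assumed effects). This supports estimation rather than testing.

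**5. Number of estimates.** The DBW rows run from Week 16 to Week 44, which is eight visits. A difference at every visit would give 3 × 8 = 24 intervals; one named visit gives 3.

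**The case against.** The best case for the plan is that description was deliberate. Protocol 10.3.9 already plans only summaries for exactly these scores, Protocol Table JAHV.8 leaves them out of the compared endpoints, and SAP 6.17 follows. With a floor of 10 patients and no multiplicity control (SAP 6.5), declining to test is reasonable, and a specific table would normally override a general rule. The argument against testing stands. It does not reconcile the objectives with the analysis: an estimate with an interval needs no test, and no text says that Table JAHV.6.9 overrides 6.1.4.

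Three stronger readings are tempting, and the documents do not support them.

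- A reader might infer that the trial cannot answer these objectives. Randomized arms will be summarised side by side, JIA category is a stratification factor, and a difference can be computed from the data collected.
- A reader might infer that nothing in the plan yields a between-arm estimate. SAP 6.1.4 and Protocol 10.3.1 would yield one, so the fault is a conflict and not silence.
- A reader might infer that results will carry no measure of uncertainty. Protocol 10.3.1 includes the SD in continuous summaries, so a crude interval could be worked out from mean, SD and n. What is missing is a planned treatment difference with its interval.

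**Conclusion.** The point holds as a mismatch between objectives and analysis, together with an internal SAP conflict. All three DBW endpoints under the two comparative objectives lack a planned between-arm estimate in Table JAHV.6.9, although 6.1.4 would require one. On the baseline defined in SAP 6.1.2, per-arm changes mix open-label response with the effect of randomized treatment, so they do not replace that estimate.

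The consequence is limited to these secondary objectives. The size of the likely interval, about 1.46 SD unadjusted or 1.50 SD on ANCOVA degrees of freedom, assumes exactly 10 ERA/JPsA patients split 5 and 5. It would be narrower with more patients. It does not describe PASI, which is analysed in JPsA alone, where the interval may be wider or not estimable.

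**What to change.** In the three DBW rows of SAP Table JAHV.6.9, replace the no-comparison entry with: baricitinib-minus-placebo difference in mean change and its 95% CI at one named visit (for example Week 44, LOCF), from ANCOVA with treatment and baseline score only, reported as estimation without a significance claim. Keep the by-visit summaries descriptive. Add that if the model cannot be fitted, as may happen for PASI, only the summaries are reported. In SAP 6.1.4, state that Table JAHV.6.9 governs these endpoints. Settle this before unblinding.

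Simply deleting the placebo comparison from the two objectives is not a good alternative. It would leave each one duplicating the non-comparative objective beside it, and it would change objectives stated in the protocol.

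The cost is one table edit, one sentence in 6.1.4 and three extra estimates. No new data are needed. Under Protocol 10.3.1, a change of analysis method that does not alter a principal feature is described and justified in the clinical study report, without an amendment. The downside is an interval that may be visibly wide.
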